STUDY POPULATION	
Patients with a supratentorial aSAH secondary to a ruptured cerebral aneurysm that has been secured by endovascular coil embolization. Study subjects must score as a WFNS SAH grade ≤ 2 post-coiling with no significant aphasia at the time of enrollment and have a significant hemorrhage burden on the initial head computed tomographic (CT) scan that demonstrates a modified-Fisher grade 3, or grade 4 (with minimal intraparenchymal blood or IVH less than 25%.)

CLINICAL SITES	
Eight to ten designated clinical sites in the USA.

PLANNED ENROLLMENT	
88 patients (44 in each treatment allocation group; Approximately 5-6 patients per site per year average)

STUDY DURATION	
3 years [2 years enrollment; 3 months primary end-point follow-up visit; 3 months data analysis and reporting of results; 1-year follow-up visit secondary endpoint].

PRIMARY SAFETY ENDPOINT	
Rate of “Major Bleeding” or “Clinically Relevant Non-Major Bleeding” as defined by the International Society of Thrombosis and Haemostasis (ISTH) between the groups from enrollment until discharge from the acute inpatient setting.

SECONDARY SAFETY ENDPOINT	
Rate of Symptomatic Intracranial Hemorrhage between the two groups from enrollment until discharge from the acute inpatient setting. A symptomatic hemorrhage is defined as a 4-point or greater increase in the NIHSS or a decrease in the GCS by 2 or more points not explained by other causes.

ADDITIONAL PRESPECIFIED SAFETY OUTCOMES TO BE ANALYZED	
Rate of any new intracranial hemorrhage between the two groups from enrollment until discharge from the acute inpatient setting.
 
Rate of Serious Adverse Events (SAEs) between the two groups from enrollment until

the 90-day follow-up visit as reported by each site and adjudicated by an independent Clinical Events Adjudication Committee (CEC).

Rate of Type II Heparin Induced Thrombocytopenia (HIT) between the two groups from enrollment until the 90-day follow-up visit

Rate of DVT or PE between the two groups from enrollment until the 90-day follow-up visit

All cause and neurological mortality rates between the two groups from enrollment until the 90-day follow-up visit

PRIMARY CLINICAL EFFECT ENDPOINT

Mean Montreal Cognitive Assessment score (MoCA) at 90 (± 10) days post enrollment.

SECONDARY ENDPOINTS:

-PRIMARY BIOMARKER ENDPOINT

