STUDY DRUG NAME
AND FORMULATION**

Unfractionated Heparin (UFH) intravenous solution at a concentration of 100 units per ml (25,000 to 50,000 units of heparin in 250 to 500 ml of 0.9% or 0.45% NaCl solution)

INTENDED USE

A prophylactic infusion of LDIVH for up to 14 days with prescribed escalated dosing until the goal aPTT value is achieved. The LDIVH infusion is intended to prevent cognitive deficits in modified-Fisher grade 3 and 4 aneurysmal subarachnoid hemorrhage survivors following endovascular coil embolization of the ruptured cerebral aneurysm. The LDIVH infusion is to be initiated 12 ± 4 hours after coiling of the aneurysm. The infusion will be started at 8 units/kg/hr (0.08 cc/kg/hr) and increased by 2 units/kg/hr every 12 hours until the goal aPTT is reached (typically 12 u/kg/hr) *Note: The goal aPTT is an institution specific aPTT value that correlates with an anti-Xa assay value of 0.1 – 0.3 IU/ml of heparin.*

STUDY SUCCESS

For the purposes of this trial, study success is defined as demonstrating a statistically significant improvement in the mean MoCA score for the LDIVH arm compared to the control arm of the study at the 90-day follow-up visit or a significant reduction in inflammatory biomarker levels in the LDIVH arm compared to the control arm. In addition, there can be no significant differences between groups in the rate of Major Bleeding or Clinically Relevant Non-Major Bleeding attributable to the LDIVH treatment.

PATIENT COMPLETION

Patient completion in the study occurs when the patient has completed his/her 1-year follow-up

visit and all case report forms (CRFs) and Imaging required by the Study Protocol have been completed OR the patient has withdrawn from the study or has been determined to be “Lost to Follow-up” and all available CRFs and Imaging have been collected and submitted to the University of Louisville. The primary endpoint is the 90-day follow-up visit and therefore the primary data-analysis will occur after this date.

**PRIMARY PRINCIPAL
INVESTIGATOR (PPI) /
SPONSOR**

[name]
Associate Professor of Neurosurgery
Chief, Vascular Neurosurgery
University of Louisville School of Medicine
Louisville, KY
[contact];
[contact]

**CO-PRINCIPAL
INVESTIGATORS (Co-PI)**

J. [name], PhD
Professor of Neurosurgery, Pathology & Physiology
University of Maryland Medical Center
Baltimore, MD

[name]
Professor and Vice Chair for Education
Department of Neurosurgery
Director, Cerebrovascular Surgery Program

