1.2 STUDY OBJECTIVES

1.2.1 Primary Objective

1. Demonstrate the safety of a low-dose intravenous infusion of unfractionated heparin (LDIVH) in aSAH patients treated with coil embolization.
2. Demonstrate a positive clinical effect of LDIVH in aSAH patients through measurement of significantly better mean Montreal Cognitive Assessment (MoCA) scores in the LDIVH treated subjects at a 90-day follow-up visit compared to control patients.

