8.5 DEFINITIONS AND MANAGEMENT OF BLEEDING / HEMORRHAGE EVENTS

We have chosen to follow formal guidelines set forth by the International Society of Thrombosis and Haemostasis for bleeding complications (Schulman S, et al. *J Thromb Haemost* 2005;3(4):692-694). The normal rate of major bleeding or clinically relevant non-major bleeding in aSAH patients with protected aneurysms is estimated at approximately 10-20% (EVD insertion/tract hemorrhages, femoral artery access complications, GI bleed, fall out of bed, nasopharyngeal feeding tube insertion, etc.).

Bleeding complications are defined as:

Any development of clinically relevant non major bleeding or major bleeding, as defined by the International Society of Thrombosis and Haemostasis (ISTH):**a) Major Bleeding (≥ 1 of the following in 24 hr time period):**

- i) Bleeding causing a fall in hemoglobin level of 2 g/dL or more, or leading to transfusion of two or more units of whole blood or red cells.
- ii) Symptomatic bleeding in a critical area or organ, such as intracranial, intraspinal, intraocular, retroperitoneal, intraarticular or pericardial, or intramuscular with compartment syndrome, and/or
- iii) Fatal bleeding

b) Clinically Relevant Non-Major Bleeding

- i) Acute or sub-acute clinically overt bleeding that does not satisfy the criteria for major bleeding and leads to physician-guided medical or surgical treatment for bleeding, or a change in antithrombotic therapy (including study drug) for bleeding.

c) Minor Bleeding

- i) All acute clinically overt bleeding events not meeting the criteria for either major bleeding or clinically relevant non-major bleeding are classified as minor bleeding.

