10. DATA ANALYSIS AND CONSIDERATIONS

10.1 Sample Size Justification and Primary Clinical Effect Analysis

The sample sizes justification is based on the combination of the pilot data that we have previously observed ([name] Unpublished) and results based on Schweizer et al. (2012). Two main outcomes, MoCA and MMSE, were compared by Schweizer et al (2012) and their validity was compared. The two measures have slightly different cut-offs for defining impairments (MoCA score <26 and MMSE score <27). In this study we will use MoCA as a primary outcome measure. Based on published data, MoCA has mean (SD) of 25.4 (2.8) with n=32. In our pilot data with small sample sizes, we observed an overall mean of 24.6 (5.4) with n=47. The separate group means were 26.4 (2.3) with n=25 and 22.7 (7.0) with n=22 in the treatment and control arms, respectively. Because the two groups were heterogeneous, we assume SD=2.5 in treatment group and SD=7.0 in control group. As hypothesized and as documented in the preliminary data, MoCA is higher in the treatment arm than in the control arm, and so we will use one-sided test procedures. The study design is that of a two group, multicenter randomized clinical trial.

Table S1: Sample sizes based on having alpha=5% and SD1=7.0 and SD2=2.5 to detect 3 unit (effect size=0.5 SD) using one-sided two-sample t test with unequal variances.

Power	N1	Total N
80%	40	80
85%	46	92
90%	54	108

Given the number of centers participating, we plan to enroll 40 evaluable subjects in each arm. Assuming 8 centers, a sample size of 80 would be realized by recruiting 10 per center. Note that we need to balance the number of treatment and controls to be equal at each center, but not necessarily having equal number of subjects at each center. However, the numbers in the tables do not adjust for loss to follow up, drop outs, the ability to adjust for covariates, or for the loss of degrees of freedom for the centers in a test or model. The discussion below addresses further aspects of the sample size consideration.

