10.4 General Statistical Plan

Patients enrolled will be presented. On-study protocol violations will also be presented. Patients who do not complete the required observations will be listed and evaluated separately as necessary. Reasons for study discontinuation and date of withdrawal from study will be presented.

Descriptive statistics related to the participant characteristics, treatment, and prognostic factors will be reported. For the continuous variables mean (95% confidence interval), median (minimum and maximum) will be reported and for discrete variables frequency and percentages will be reported. For continuous variables a two sample t-test/rank sum test will be used to compare between groups. A Chi-square test will be used for establishing association between categorical variables. For example MoCA will be compared between two groups using a contrast based t test in addition to simple two sample test either based on a linear regression or Mixed model approach when multiple observations on sample subject is considered. A discrete outcome such as prevalence of 'have any fever' between treatment and control arms will be tested using a logistic regression analyses. In order to examine the significant prognostic factors, we will use the multiple linear and logistic regression models in multi-variable setting.

A significance level of 5% will be used to declare results significant. For selected primary outcome variables we will report adjusted p-values for multiplicity in addition to unadjusted p-values. All calculations will be performed with methods described in Walker et al. (2010), Rosner (2010) and with SAS statistical software (SAS, 2003).

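### The success definition accepts a non-significant bleeding difference as its safety condition, yet with 44 per arm a true doubling of bleeding would be non-significant in about 45–73% of trials

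*Protocol*

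**What the plan says.** Section 1.2.1 of the protocol lists as the first primary objective: "Demonstrate the safety of a low-dose intravenous infusion of unfractionated heparin (LDIVH) in aSAH patients treated with coil embolization". The primary safety endpoint in section 1.1 is the rate of ISTH major or clinically relevant non-major bleeding, compared between groups "from enrollment until discharge from the acute inpatient setting". It carries no attribution filter.

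The study-success entry in section 1.1 asks for a significant MoCA or biomarker benefit and then adds the safety condition: "there can be no significant differences between groups in the rate of Major Bleeding or Clinically Relevant Non-Major Bleeding attributable to the LDIVH treatment".

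Section 8.5 gives the background: "The normal rate of major bleeding or clinically relevant non-major bleeding in aSAH patients with protected aneurysms is estimated at approximately 10-20" per cent. Planned enrollment is "88 patients (44 in each treatment allocation group"). On testing, section 10.4 says "A significance level of 5% will be used to declare results significant" and "A Chi-square test will be used for establishing association between categorical variables". It does not say whether the bleeding test is one- or two-sided.

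Section 10.1 derives the sample size from mean MoCA ("we assume SD=2.5 in treatment group and SD=7.0 in control group") and supports it with a calculation on MoCA of 20 or below. It contains no bleeding calculation.

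**The concern.** A test that does not reject shows only that the data were too few or too variable to establish a difference. Used as a success condition, it rewards imprecision: the smaller or noisier the trial, the easier the condition is to meet. The treatment is an anticoagulant infusion given after an intracranial hemorrhage, and the trial is meant to inform whether a Phase III study is warranted. A real and sizeable excess of bleeding could be recorded as meeting the safety condition.

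There is also a wording problem. The success clause speaks of attribution to LDIVH, whereas the primary safety endpoint compares all such bleeds. The protocol does not say whether attribution filters the events or qualifies the difference.

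**Working it through.** **Inputs.** 44 per arm (section 1.1). The bleeding window closes at acute discharge, so the 10% allowance for 90-day dropout is not deducted. Background 10%, 15% and 20% (range in section 8.5). Chi-square at 5% (section 10.4). Two-sided is an assumption, and one-sided is shown as well. A doubling is used as the illustration of harm.

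**1. The plan's own figure.** Table S1 gives 80% power at 40 per arm for 3 MoCA points, SDs 7.0 and 2.5, one-sided 5%. SE = √((7.0² + 2.5²)/40) = √1.381 = 1.175, and 3/1.175 = 2.55. The noncentral t gives 80.8% (85.5% at 46, 90.2% at 54). The table is reproduced. It concerns MoCA only.

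**2. Chance that a true doubling passes.** Normal approximation for 15% against 30%:
- Pooled rate 0.225; SE under no difference = √(2 × 0.225 × 0.775/44) = 0.0890.
- SE under the alternative = √((0.15 × 0.85 + 0.30 × 0.70)/44) = 0.0876.
- Power = Φ((0.15 − 1.96 × 0.0890)/0.0876) = Φ(−0.28) = 39%, so 61% pass.

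Exact enumeration of the two binomials gives these chances of a non-significant result:

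| Control → LDIVH | Chi-square, two-sided 5% | Chi-square, one-sided 5% | Fisher, two-sided 5% |
|---|---|---|---|
| 10% → 20% | 73% | 62% | 83% |
| 15% → 30% | 59% | 47% | 71% |
| 20% → 40% | 45% | 33% | 55% |

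For 80% power to detect a doubling (two-sided), the trial would need 199, 121 or 82 per arm.

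**3. What passing data look like.** 4/44 control against 8/44 LDIVH: chi-square p = 0.21, excess +9 points, 95% CI −5 to +23. 7/44 against 14/44: p = 0.08, excess +16 points, 95% CI −2 to +33. Both meet the condition. With 4 control events, LDIVH needs 11 before the two-sided chi-square fails it.

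**4. The attribution wording.** If only LDIVH-attributable bleeds counted and controls could have none, the control rate would be 0%. The two-sided chi-square would then pass 35%, 9% or 2% of the time at LDIVH-attributable rates of 10%, 15% or 20%; 4 events against 0 already gives p = 0.041.

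**5. What 44 per arm can exclude.** One-sided 95% upper limit for the excess at equal observed rates p: 1.645 × √(2p(1 − p)/44) = +10.5, +12.5 and +14.0 points at p = 10%, 15% and 20%.

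**6. Cost of a margin rule.** With equal true rates of 10%, 15% or 20%, the chance that this upper limit (computed from the observed rates) lies below an illustrative margin is:
- 10-point margin: 47%, 37%, 32%
- 15-point margin: 78%, 64%, 56%

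**7. Does the toxicity stopping rule help?** Table S2 is a within-arm boundary for grade 3 or 4 events at 33%. Applied to bleeding alone (reading its overlapping row as 38–40 subjects), it would stop with probability 0.3%, 3% and 18% at true rates of 20%, 30% and 40%. It does not close the gap.

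**The case against.** A Phase II trial need not be powered for bleeding, and the clause does not act alone. Success also requires a significant MoCA or biomarker result. The protocol follows symptomatic and any new intracranial hemorrhage, SAEs, HIT, DVT/PE and mortality, and it has a DSMB and a medical safety monitor. All of this stands, so the Phase III decision does not rest on one p-value. None of it repairs a success definition that treats non-significance as the safety condition, and an SAP cannot cure a rule already fixed in the protocol.

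Three stronger readings are tempting and are not supported:

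- A reader might infer that a doubling would usually pass. That holds at 10% and 15% background under a two-sided test. At 20% the figure is 45%. One-sided, it holds only at 10%. The protocol's sample-size tests are one-sided, so that reading cannot be dismissed.
- A reader might infer that controls cannot have an attributable event and that the clause is therefore laxer still. That is only one reading, since the words may equally qualify the difference. It is incompatible with a 10–20% control rate and, for the same added 10, 15 or 20 points, would make the rule stricter (step 4). Relatedness calls are also adjudicated by the CEC (section 8.1). What remains is an ambiguity and a mismatch with the endpoint.
- A reader might infer that a margin rule costs nothing. Step 6 shows that an equally safe drug would often fail it.

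**Conclusion.** The point holds. Non-significance in this trial cannot demonstrate safety, because a true doubling of bleeding would go undetected in about 45–73% of trials across the protocol's background range (two-sided 5% chi-square), or 33–62% if the test is one-sided. Fisher's test would raise the two-sided figures to 55–83%.

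These figures rest on 44 analyzed patients per arm, independent binomial events, the 10–20% range applied to controls, and all qualifying bleeds being counted. A doubling is an illustration; the protocol does not say what excess would be tolerable. The attribution wording needs clarifying, but no size can be put on its effect until its meaning is fixed.

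**What to change.** In the study-success entry of section 1.1, delete the absence of a significant difference as the demonstration of safety. In its place:

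1. Compare all CEC-adjudicated major or clinically relevant non-major bleeds from enrollment to acute discharge, regardless of attribution, as the primary safety endpoint already does.
2. Report the risk difference (LDIVH minus control) with its confidence interval.
3. State the largest excess not excluded, using the one-sided 95% upper limit. Readers should expect about +10.5, +12.5 or +14.0 points at equal observed rates of 10%, 15% or 20%.
4. Align the first primary objective, so that it speaks of estimating bleeding risk unless a margin is set.

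If the sponsor wants a pass/fail rule, the maximum acceptable excess is its clinical choice and must be fixed before unblinding. The protocol should then disclose that a truly equal-risk drug would pass only about 32–47% of the time at an illustrative 10-point margin and 56–78% at 15 points. Neither margin is a proposal.

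Items 1 to 4 change wording in the protocol, and in the SAP if one exists. They add no patients. The cost is a more modest safety claim.

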1. STUDY SYNOPSIS AND OBJECTIVES

1.1 STUDY SYNOPSIS

STUDY TITLE	Aneurysmal Subarachnoid hemorrhage Trial RandOmizing Heparin (ASTROH)
PRIMARY OBJECTIVES	The primary objective of this study is to investigate the safety and clinical effect of a continuous low-dose intravenous unfractionated heparin (LDIVH) infusion for the prevention of aneurysmal subarachnoid hemorrhage (aSAH) induced neurocognitive dysfunction. The rate of “Major Bleeding” or “Clinically Relevant Non-Major Bleeding” as defined by the International Society of Thrombosis and Haemostasis (ISTH) between the LDIVH and the control group will be compared. The mean Montreal Cognitive Assessment (MoCA) scores obtained at a 90-day follow-up visit will be compared between LDIVH treated patients and controls. We expect the results of this study to inform on whether a properly powered Phase III study evaluating a LDIVH infusion for aSAH is warranted.
SECONDARY OBJECTIVES	Increased blood and CSF levels of certain inflammatory biomarkers have been correlated to aSAH patients with poor clinical outcomes. Unfractionated heparin (UFH) has known anti-inflammatory actions. As a result, a secondary objective of this study will be to evaluate whether LDIVH can reduce blood and CSF inflammatory biomarker levels compared to controls and whether there is any association between inflammatory biomarker levels and cognitive outcomes in aSAH.
STUDY DESIGN	Investigator initiated and sponsored, multicenter, prospective, 1:1 randomized, open-label, blinded adjudication phase II study. Study patients randomized to the LDIVH arm will receive normal standard of care (SOC) plus a continuous low-dose intravenous infusion of UFH for up to 14 days. During the 14-day infusion, the LDIVH arm study subjects will not receive any chemical deep venous thrombosis

	
(DVT) prophylaxis but may resume chemical DVT prophylaxis after the 14-day infusion is complete. Study patients randomized to the control arm will receive the normal standard of care (SOC), which will be UFH 5,000 units, twice daily.

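### Study success treats a non-significant bleeding difference as demonstrated safety, although 44 patients per arm cannot reliably detect even a doubling of bleeding

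*Protocol*

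**What the plan says.** The Study Success entry in Protocol 1.1 asks for a significant benefit on 90-day MoCA or on inflammatory biomarkers, and then adds one safety condition: "there can be no significant differences between groups in the rate of Major Bleeding or Clinically Relevant Non-Major Bleeding". The sentence ends by limiting this to differences attributable to LDIVH. No other safety condition for success is given.

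That condition serves the first primary objective in 1.2.1: "Demonstrate the safety of a low-dose intravenous infusion of unfractionated heparin (LDIVH") in coiled aSAH patients. The same bleeding composite is the primary safety endpoint in 1.1, counted from enrollment to discharge from the acute inpatient setting.

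The design is a "1:1 randomized, open-label, blinded adjudication phase II study" with "88 patients (44 in each treatment allocation group"). Section 8.5 gives the background rate of the composite, in per cent: major or "clinically relevant non-major bleeding in aSAH patients with protected aneurysms is estimated at approximately 10-20".

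Section 10.1 sizes the trial on the MoCA mean, with the proportion scoring 20 or less on MoCA as a supporting calculation. Section 10.4 sets a general 5% significance level and names a chi-square test for categorical variables. No section states a power, a tolerable excess or a confidence limit for bleeding.

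**The concern.** A non-significant result supports a claim of safety only if the trial would probably have detected an excess that matters. Nothing in the protocol shows that it would. The condition also rewards imprecision: the fewer patients and events there are, the easier it is to meet.

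The treatment is an infusion of up to 14 days of an anticoagulant, begun soon after an intracranial hemorrhage. The results are meant to inform whether a Phase III trial is warranted. If the condition is met, the report can say that safety was demonstrated while its own interval still allows a large bleeding excess.

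**Working it through.** **Inputs.** 44 per arm, 1:1 (1.1). Control bleeding rate 10-20% (8.5). Level 5% and chi-square (10.4). Bleeding is counted to discharge, so all 44 per arm are taken as evaluable. A doubling means 10 vs 20%, 15 vs 30% or 20 vs 40%.

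**The plan's own figure.** Table S1 uses a one-sided 5% t test with unequal variances, SDs 7.0 and 2.5, and a difference of 3. The normal formula gives n = (7.0² + 2.5²)(1.645 + 0.842)²/3² = 37.95. The noncentral t calculation gives power of 79.9% at 39 and 80.8% at 40 per arm. Table S1's 40 per arm reproduces, and it concerns MoCA only.

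**Hand check for bleeding, 15 vs 30%, two-sided.**
- Pooled rate 0.225. SE under no difference = √(2 × 0.225 × 0.775/44) = 0.0890.
- Difference needed for significance = 1.96 × 0.0890 = 0.1745.
- SE under the alternative = √((0.15 × 0.85 + 0.30 × 0.70)/44) = 0.0876.
- Power = Φ((0.15 − 0.1745)/0.0876) = Φ(−0.28) = 0.39, so the condition is met about 61% of the time.

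**Exact enumeration.** Summing the product of the two binomial probabilities over all 45 × 45 tables gives the probability that the condition is met:

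| True rates, control vs LDIVH | Chi-square, two-sided 5% | Chi-square, one-sided 5% | Fisher, two-sided 5% |
|---|---|---|---|
| 10 vs 20% | 73% | 62% | 83% |
| 15 vs 30% | 59% | 47% | 71% |
| 20 vs 40% | 45% | 33% | 55% |

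For a true tripling, two-sided chi-square gives 32% (10 vs 30%), 11% (15 vs 45%) and 2% (20 vs 60%).

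**Size needed.** For 80% power to detect a doubling, two-sided, the trial would need 199, 121 or 82 per arm at base rates of 10, 15 and 20%. One-sided, it would need 157, 95 or 64.

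**What equal observed rates would show.** Take 7/44 in each arm (15.9%), an illustration inside the stated range. The Wilson limits at one-sided 95% are 0.0886 and 0.2691. The Newcombe upper limit for the difference is √((0.2691 − 0.1591)² + (0.1591 − 0.0886)²) = √(0.0121 + 0.0050) = 0.131. Even identical observed rates leave an excess of about 13 points open.

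**The case against.** **This is phase II and safety is watched elsewhere.** The trial has a DSMB that can recommend stopping, event adjudication, a medical safety monitor, toxicity boundaries and other prespecified safety comparisons. All of this stands and lessens the practical consequence. None of it repairs the success rule. The boundary in 10.5.2 tests grade 3 or 4 toxic events within each arm against 33%; it does not compare bleeding between arms. The phase II purpose is a reason to estimate, not to define success by non-significance.

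**The test for bleeding is inferred.** This also stands. Section 10.4 names chi-square and also mentions logistic regression for a discrete outcome, and 10.1 uses a one-sided binomial test for severe cognitive impairment. The SAP may settle the matter, so the results are shown for three tests. Single examples depend on the choice: 7/44 vs 14/44 gives z = 1.75, which meets the condition two-sided (p = 0.080) and fails it one-sided (p = 0.040).

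**Stronger readings that the protocol does not support.**
- A reader might infer that the rule has no direction, so that significantly less bleeding on LDIVH would fail it. The words on attribution to LDIVH point to excess bleeding. They do not rescue the rule, because they supply no margin or power and do not say how attribution enters a comparison of rates.
- A reader might infer that benefit is held to a laxer threshold than harm, because for MoCA the protocol says "so we will use one-sided test procedures". Sidedness for bleeding is not stated, so the asymmetry cannot be asserted.
- A reader might infer that a tripling would usually slip through. At 32%, 11% and 2%, it usually would not.
- A reader might infer that success by itself recommends Phase III. The synopsis says only that the results will inform that decision.

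**Conclusion.** The point holds. The only safety condition for study success is the absence of a significant bleeding difference, which cannot support the stated objective of demonstrating safety at this sample size. With 44 evaluable patients per arm and the protocol's background rate, a true doubling would meet the condition about 45-73% of the time under the two-sided chi-square test. Across the three tests examined the range is about 33-83%. The condition gives real protection against a tripling when the base rate is 15-20%, and less at 10%. The conclusion does not depend on which test the SAP names, since none of the three detects a doubling reliably.

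**What to change.** - Remove the non-significance clause from Study Success in 1.1.
- Name as the primary safety result the LDIVH minus control difference in Major or Clinically Relevant Non-Major Bleeding, with its 95% confidence interval.
- Reword the first primary objective in 1.2.1 as estimating the bleeding excess on LDIVH.
- State that a non-significant difference will not be read as evidence of safety.

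These are wording changes to the protocol and do not alter sample size or procedures. The cost is a less favourable safety claim.

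The sponsor may instead keep a safety condition in the form of an upper confidence limit below a margin fixed in advance. That changes the definition of success and has a price at this size. The protocol gives no margin, so as an assumed example take 15 points with a one-sided 95% Newcombe limit. With no true excess, it would be met only 72%, 61% and 54% of the time at base rates of 10, 15 and 20%. A drug with no excess bleeding would therefore fail 28-46% of the time. Estimation without a margin suits 88 patients better.
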